10.3 BLOOD PRESSURE MEASUREMENT PROCEDURE

Blood pressure measurements should be performed on the same arm and, if possible, by the same person. The machines or devices to be used for blood pressure measurement should be certified. The machines to be used for blood pressure measurement should be certified. The same method and device must be used throughout the trial for a patient i.e. if a patient receives the first blood pressure measurement for example with an electronic device, the same method and device should be used throughout the study for this patient (without switching to manual blood pressure measurement). On the other hand, inter-patient variability is acceptable, i.e. a study site is allowed to consistently use an electronic device to measure the blood pressure in a given patient throughout the study and a manual technique in another patient. After patients have rested quietly, in the seated position for five minutes, three blood pressure measurements will be taken two minutes apart and all three results have to be entered in the eCRF.

In case of a suspected “white coat effect” it is recommended to repeat the measurement in a pleasant condition after sufficient rest. Values from self-blood pressure measurement (SBPM) communicated from patient to investigator is not considered valuable for study related decisions.

10.4

TIME SCHEDULE FOR PHARMACOKINETIC (PK),
BLOOD SAMPLING

Table 10.4: 1 Time schedule for PK, [REDACTED] blood sampling for Part I

Cycle	Visit	Day	Time Point	CRF Time / planned time (hh:min)	PK: BI 836880	[REDACTED]
1, 2	1	1	Before start of BI 836880 infusion	-0:05	X	[REDACTED]
			Start of BI 836880 infusion	0:00		[REDACTED]
			Immediately after end of infusion*	1:00**	X	[REDACTED]
			0.5h after the end of infusion	1:30	X	[REDACTED]
			1.5h after the end of infusion	2:30	X	[REDACTED]
			3.5h after the end of infusion	4:30	X	[REDACTED]
			6.5h after the end of infusion	7:30	X	[REDACTED]
	2a	2	24h after the start of infusion	24:00	X	[REDACTED]
	2b	3	48h after the start of infusion	48:00	X	[REDACTED]
	3	8	7 days after start of infusion	168:00	X	[REDACTED]
	4	15	14 days after start of infusion	336:00	X	[REDACTED]
3	1	1	Before start of BI 836880 infusion	-0:05	X	[REDACTED]
			Start of BI 836880 infusion	0:00		[REDACTED]
			Immediately after end of infusion*	1:00**	X	[REDACTED]
	2a	2	24h after the start of infusion	24:00	X	[REDACTED]
4	1	1	Before start of BI 836880 infusion	-0:05	X	[REDACTED]
			Start of BI 836880 infusion	0:00		[REDACTED]
			Immediately after end of infusion*	1:00**	X	[REDACTED]
			0.5h after the end of infusion	1:30	X	[REDACTED]
			1.5h after the end of infusion	2:30	X	[REDACTED]

Clinical Trial Protocol

Page 93 of 110

Proprietary confidential information © 2019 Boehringer Ingelheim International GmbH or one or more of its affiliated companies

Cycle	Visit	Day	Time Point	CRF Time / planned time (hh:min)	PK: BI 836880	
			3.5h after the end of infusion	4:30	X	
			6.5h after the end of infusion	7:30	X	
	2a	2	24h after the start of infusion	24:00	X	
	3	8	7 days after start of infusion	168:00	X	
	4	15	14 days after start of infusion	336:00	X	
5-12	1	1	Before start of BI 836880 infusion	-0:05	X	
			Start of BI 836880 infusion	0:00		
EoT					X	
Safety follow-up					X	

* within 5 min after the end of infusion

** PTM of 1:00 according to an infusion duration of 60 min. If the infusion duration should be shorter (or longer), the PK sample has to be taken in any case immediately after the end of the infusion/ the ECG has to be conducted shortly before end of infusion and the actual sampling time needs to be recorded in the eCRF. Subsequent PK samples (in C1, C2 and C4) have to be taken 0.5h, 1.5h, 3.5h and 6.5h after the end of the infusion.

Table 10.4: 2 Time schedule for PK, [REDACTED] blood sampling for Part II

Cycle	Visit	Day	Time Point	CRF Time / planned time (hh:min)	PK BI 836880 BI 754091	
1	1	1	Before start of BI 754091 infusion	-0:05	X	
			Start of BI 754091 infusion	0:00		
			After end of BI 754091 infusion	1:00*	X	
			Start of BI 836880 infusion	1:15		
			After end of BI 836880 infusion	2:15*	X	
			6 hours after start of BI 754091 infusion (3:45 after end of BI 836880 if	6:00	X	

Clinical Trial Protocol

Page 94 of 110

Proprietary confidential information © 2019 Boehringer Ingelheim International GmbH or one or more of its affiliated companies

Cycle	Visit	Day	Time Point	CRF Time / planned time (hh:min)	PK BI 836880 BI 754091	
			no infusion delay)			
2a	2		24h after start of BI 754091 infusion	24:00	X	
3	8		7 days after start of BI 754091 infusion	168:00	X	
4	15		14 days after start of BI 754091 infusion	336:00	X	
2, 3	1	1	Before start of BI 754091 infusion	-0:05	X	
			Start of BI 754091 infusion	0:00		
			After end of BI 754091 infusion	1:00*	X	
			Start of BI 836880 infusion	1:15		
			After end of BI 836880 infusion	2:15*	X	
4	1	1	Before start of BI 754091 infusion	-0:05	X	
			Start of BI 754091 infusion	0:00		
			After end of BI 754091 infusion	1:00*	X	
			Start of BI 836880 infusion	1:15		
			After end of BI 836880 infusion	2:15*	X	
			6 hours after start of BI 754091 infusion (3:45 after end of BI 836880 if no infusion delay)	6:00	X	
	2a	2	24h after start of BI 754091 infusion	24:00	X	
	3	8	7 days after start of BI 754091	168:00	X	

Proprietary confidential information © 2019 Boehringer Ingelheim International GmbH or one or more of its affiliated companies

Cycle	Visit	Day	Time Point	CRF Time / planned time (hh:min)	PK BI 836880 BI 754091	
			infusion			
	4	15	14 days after start of BI 754091 infusion	336:00	X	
5, 6	1	1	Before start of BI 754091 infusion	-0:05	X	
			Start of BI 754091 infusion	0:00		
			After end of BI 754091 infusion	1:00*	X	
			Start of BI 836880 infusion	1:15		
			After end of BI 836880 infusion	2:15*	X	
7-12	1	1	Before start of BI 754091 infusion	-0:05	X	
EoT					X	
Safety follow-up					X	

* within 5 min after the end of infusion

10.5 STATISTICAL APPENDIX INCLUDING MODEL PERFORMANCE AND DATA SCENARIOS

The model was assessed by two different metrics: hypothetical on-study data scenarios and long-run operating characteristics. The simulations for scenarios and operating characteristics were produced using R version 3.4.2.

10.5.1 Part I (BI 836880 monotherapy dose finding part)

Hypothetical data scenarios

Hypothetical data scenarios are shown in [Table 10.5.1: 1](#). These scenarios reflect potential on-study data constellations and related escalation as allowed by the model. For each scenario, the probability of overdose for the current dose, as well as the next potential dose and related probabilities of under-dosing, target dose, and over-dosing are shown.

For example, scenario 1 represents the case that no DLT is observed in the first three patients at the starting dose of 360 mg. In this case, the next optimal dose, i.e. the dose with the highest probability of being in the target interval, is 720 mg. Similarly scenario 4 represents the case where no DLTs are observed, and the next optimal dose recommended is 720 mg according to BLRM since no higher dose is available.

Scenarios 5 illustrates the case where low dose cohorts have no DLT and the highest dose level 720 mg/kg has 1 DLT, in such cases, BLRM would continue to assign patients on 720 mg/kg,

In scenario 6, two DLT is observed already in the patient. In this case, the model recommends de-escalation to 360 mg.

Table 10.5.1: 1 Hypothetical data scenarios

Scenario	Dose (mg)	# DLT	# Pat	Current Dose: P(OD)	Next Recommended Dose	Next Dose		
						P(UD)	P(TD)	P(OD)
1	360	0	3	0.005	720	0.728	0.213	0.059
2	360	1	3	0.052	720	0.406	0.416	0.179
3	360	2	3	0.241	360	0.350	0.410	0.241
4	360	0	3					
	720	0	3	0.016	720	0.831	0.152	0.016
5	360	0	3					
	720	1	3	0.093	720	0.561	0.346	0.093

6	360	0	3						
	720	2	3	0.319	360		0.865	0.114	0.021

Operating characteristics

Operating characteristics are a way to assess the long-run behaviour of a model by illustrating the precision of the design in estimating the MTD. Under an assumed true dose-toxicity curve, metrics such as the probability of recommending a dose with true DLT rate in the target interval can be approximated via simulation. [Table 10.5.1: 2](#) describes 5 assumed true dose-toxicity scenarios which were used to assess the operating characteristics of the model. These scenarios reflect a wide range of possible cases as follows:

- Scenario 1: aligned with prior means
- Scenario 2: high-toxicity scenario
- Scenario 3: low-toxicity scenario
- Scenario 4: non-logistic dose-toxicity scenario
- Scenario 5: low-toxicity followed by high-toxicity
- Scenario 6: super high-toxicity scenario

Table 10.5.1: 2 Assumed true dose-toxicity scenarios

Scenario		Dose (mg)	
		360	720
1 (Prior)	P(DLT)	0.069	0.154
2 (High Tox)		0.321	0.500
3 (Low Tox)		0.039	0.180
4 (Non-Logistic)		0.280	0.360
5 (Low-High)		0.180	0.317
6 (Super High Tox)		0.580	0.769

* Additional dose level 1250mg added (assumed true tox probability of 0.444, 0.603, 0.250, 0.380 and 0.600 under scenarios 1-5 respectively) to allow R code to run. For scenario 6, additional dose level 120mg added (assumed true tox probability of 0.26) to allow R code to run.

For each of these scenarios, 1000 trials were simulated. It was then assessed how often a dose was declared as MTD with true DLT rate in the under-, targeted or over-dose range. Furthermore, the average, minimum and maximum number of patients per trial and the average number of DLTs per trial are reported. Results are shown in [Table 10.5.1: 3](#).

Table 10.5.1: 3 Simulated operating characteristics

Scenario	% of trials declaring an MTD with true DLT rate in				# Patients	# DLT
	underdose	Target dose	Overdose	STOPPED		
1	72.6	0.0	25.7	1.7	11.4(3-24)	2.3(1-8)
2	0.0	40.5	19.3	40.2	8.3(3-27)	3.4(1-10)
3	10.9	88.4	0.0	0.7	11.7(3-33)	1.8(1-6)
4	0.0	29.7	44.9	25.4	9.3(3-24)	3.0(1-12)
5	0.0	83.3	5.3	11.4	10.3(3-21)	3.1(1-8)
6	0.0	46.4	11.6	42.0	8.7(3-18)	4.1(2-9)

In Scenario 1, which reflects the case that the true dose-toxicity is aligned with prior means, 72.6% of the simulated trials declared a dose as MTD with true DLT rate under the targeted dose range, since there is no dose with assumed true toxicity probability in the target interval, therefore it is logical that none of the trials declares a MTD with true tox probability in the target interval. In many cases the model chooses that dose as MTD that is closest to the target interval, this is 720mg with assumed tox probability of 0.154, since 0.154 is very close to the target interval.

Scenario 2 (high-toxicity scenario) shows, that when the true DLT rate is high, i.e. the majority dose levels with true DLT rate above the target interval, 40.5% of the simulated trials declared a dose as MTD with true DLT rate in the targeted dose range. The starting dose has already >32.1% probability of observing at least 2 DLTs out of 3 patients or 1 DLT out of 2 patients in the first cohort. This contributes to the high percentage (40.2%) of all simulated trials for which the trial is stopped, since none of the doses is considered tolerable anymore. This is an expected situation for a high-toxicity scenario.

Scenarios 3 and 5 show that when the true DLT rate is low and low-high, most of the simulated trials declared a dose as MTD with true DLT rate in the targeted dose range.

Scenario 4 shows, that when the true DLT rate is non-logistic, then more likely the model will declare a overdose as MTD.

Scenario 6 shows that when the true DLT rate is super high, 42% of simulated trials stopped, since none of the doses is considered tolerable anymore. This is an expected situation for a super high-toxicity scenario.

The mean patient numbers range from 8.3 patients (Scenario 2) to 11.7 (Scenario 3) during the simulation. This shows that the planned maximum of 9 patients is reasonable.

In summary, the considered data scenarios show a reasonable behaviour of the model and the operating characteristics demonstrate a good precision of MTD determination.

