4.1.3 Dose-finding scheme

The dose is planned to be tested in cohorts at pre-defined provisional dose levels. The provisional dose levels to be assigned to different cohorts of patients are listed in [Table 4.1.3:](#)

Proprietary confidential information © 2019 Boehringer Ingelheim International GmbH or one or more of its affiliated companies

1 and 4.1.3: 2. Intermediate or lower dose levels may be investigated if agreed in the SMC, depending on the number of DLTs observed in the trial.

In Part II, increasing doses of BI 836880 will be administered in combination with BI 754091 at 240 mg. The dose of BI 754091 may also be titrated based on DLTs and the overall safety profile of the combination.

Table 4.1.3: 1 Example of dose escalation in Part I*

Dose level	Proposed dose of BI 836880	Increment from previous dose
0	360 mg	Starting dose
1	720 mg*	100%

*Actual dose assignments for a cohort will be communicated separately as determined by the SMC. Intermediate dose level(s) may be investigated depending on the latest DLT rate estimate. Dose levels which are higher than the recommended dose in trial 1336-0001 (720 mg) will not be investigated.

Table 4.1.3: 2 Example of dose escalation in Part II*

Dose level	Proposed dose of BI 836880	Proposed dose of BI 754091	Increment from previous dose (BI 836880)
0	120 mg*	240 mg*	Starting dose
1	360 mg*	240 mg*	200%
2-a	500 mg*	240 mg*	39% (from 360 mg)
2-b	720 mg*	240 mg*	100% (from 360 mg)

*Actual dose assignments for a cohort will be communicated separately as determined by the SMC. Intermediate dose level(s) may be investigated depending on the latest DLT rate estimate. Dose levels which are higher than the recommended dose in trial 1336-0011 will not be investigated. For dose level 2, level 2-a or 2-b will be investigated based on the information from trial 1336-0011.

There will be no dose escalations of BI 836880 or BI 754091 in any one patient.

When the last patient in each cohort completes Cycle 1, the SMC will evaluate the available data. The SMC will review all safety data including, but not limited to, DLTs and all CTCAE Version 5 Grade ≥ 2 toxicity data during cycle 1. Updated safety data on other ongoing patients, including data beyond cycle 1, will be discussed as well. Based on that, a decision on the next dose level to be tested will be made.

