10.5.2 Part II (BI 836880 and BI 754091 combination dose finding)

Hypothetical data scenarios

Hypothetical data scenarios are shown in [Table 10.5.2: 1](#). These scenarios reflect potential on-study data constellations and related escalation as allowed by the model. For each scenario, the probability of overdose for the current dose combination, as well as the next potential dose combination and related probabilities of under-dosing, target dose, and over-dosing are shown.

Table 10.5.2: 1 Hypothetical data scenarios

Scenario	Dose (mg)	# DLT	# Pat	Current Dose: P(OD)	Next Recommended Dose	Next Dose		
						P(UD)	P(TD)	P(OD)
1	120/240	0	3	0.054	360/240	0.413	0.339	0.248
2	120/240	1	3	0.228	120/240	0.336	0.436	0.228
3	120/240	2	3	0.528	NA	NA	NA	NA
4	120/240	0	3					
	360/240	0	3	0.085	360/240	0.609	0.306	0.085
5	120/240	0	3					
	360/240	1	3	0.295	120/240	0.627	0.324	0.049
6	120/240	0	3					
	360/240	2	3	0.602	120/240	0.408	0.440	0.152

For example, scenario 1 represents the case that no DLT is observed in the first three patients at the starting dose combination of 120/240 mg/kg. In this case, the next optimal dose combination, i.e. the dose combination with the highest probability of being in the target interval, is the next dose combination, i.e., 360/240 mg/kg. Scenarios 5 illustrates the case where low dose combination cohorts have no DLT and the highest dose combination level 360/240 mg/kg has 1 DLT, in such cases, BLM would de-escalate and put patients on 120/240 mg/kg. In scenarios 3, two DLT is observed already in the patient. In this case, the model recommends stopping the trial because of high overdose probabilities.

Operating characteristics

Operating characteristics are a way to assess the long-run behaviour of a model by illustrating the precision of the design in estimating the MTD. Under an assumed true dose-toxicity curve, metrics such as the probability of recommending a dose combination with true DLT rate in the target interval can be approximated via simulation. [Table 10.5.2: 2](#) describes 5 assumed true dose-toxicity scenarios which were used to assess the operating characteristics of the model. These scenarios reflect a wide range of possible cases as follows:

- Scenario 1: aligned with prior means
- Scenario 2: high-toxicity scenario
- Scenario 3: low-toxicity scenario
- Scenario 4: non-logistic dose-toxicity scenario
- Scenario 5: low-toxicity followed by high-toxicity
- Scenario 6: super high-toxicity scenario

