Table 10.5.2: 2 Assumed true dose-toxicity scenarios

Scenario		Dose (mg)		
		120/240	360/240	720/240
1 (Prior)	P(DLT)	0.209	0.318	0.680
2 (High Tox)		0.291	0.327	0.516
3 (Low Tox)		0.054	0.128	0.190
4 (Non-Logistic)		0.145	0.290	0.505
5 (Low-High)		0.128	0.169	0.550
6 (Super High Tox)		0.489	0.580	0.769

Table 10.5.2: 3 Simulated operating characteristics

Scenario	% of trials declaring an MTD with true DLT rate in				# Patients	# DLT
	underdose	Target dose	overdose	STOPPED		
1	5.9	76.9	3.8	13.4	11.9 (3-30)	3.3 (1-10)
2	0.0	64.6	9.5	25.9	10.3 (3-30)	3.4 (1-11)
3	68.1	29.2	0.0	2.7	14.6 (3-42)	1.8 (0-8)
4	66.3	7.5	20.8	5.4	11.8 (3-27)	2.8 (1-9)
5	62.2	10.6	23.4	3.8	11.9 (3-27)	2.7 (1-7)

6	0.0	24.4	26.5	49.1	11.0 (3-27)	4.3 (1-10)
---	-----	------	------	------	-------------	------------

In scenario 1, which reflects the case that the true dose-toxicity is aligned with prior means, 76.9% of the simulated trials declared a dose as MTD with true DLT rate in the targeted dose range.

In Scenario 2 (high-toxicity scenario), 64.6% of the simulated trials declared a dose as MTD with true DLT rate in the targeted dose range.

In Scenarios 1 and 2, the starting dose has already >12.0% probability of observing at least 2 DLTs out of 3 patients or 1 DLT out of 2 patients in the first cohort. This contributes to the high percentage of all simulated trials for which the trial is stopped, since none of the doses is considered tolerable anymore. This is an expected situation for assumed dose-toxicity scenarios.

In Scenarios 3-5, there is/are one or two dose(s) with assumed true toxicity probability in the underdosing interval [0.00, 0.16), in some cases the model chooses that dose as MTD that is closest to the target interval, which results in certain percentage of trials with an MTD with true DLT rate in underdosing interval.

Scenario 6 shows that when the true DLT rate is super high, 49.1% of simulated trials stopped, since none of the doses is considered tolerable anymore. This is an expected situation for a super high-toxicity scenario.

The mean patient numbers range from 10.3 patients (Scenario 2) to 14.6 (Scenario 3) during simulation. This shows that the planned maximum of 12 patients is reasonable.

In summary, the considered data scenarios show a reasonable behaviour of the model and the operating characteristics demonstrate a good precision of MTD determination.

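### The operating characteristics in Appendix 10.5 do not describe the listed dose levels: five result cells cannot arise, stopping in the very toxic scenario is understated, and the size and precision statements do not follow

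*Protocol*

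**What the plan says.** **Part I.** Table 10.5.1: 2 lists 360 and 720 mg. Its footnote adds levels so that the program would run: "Additional dose level 1250mg added (assumed true tox probability of 0.444, 0.603, 0.250, 0.380 and 0.600 under scenarios 1-5 respectively", and "For scenario 6, additional dose level 120mg added (assumed true tox probability of 0.26) to allow R code to run". Table 10.5.1: 3 then gives the percentage of trials declaring an MTD in the underdose, target or overdose range, without saying at which dose.

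**Part II.** Table 10.5.2: 2 lists 120/240, 360/240 and 720/240 mg, with no footnote on added levels. Of scenario 6 the text says "49.1% of simulated trials stopped, since none of the doses is considered tolerable anymore".

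**Permitted doses (Section 4.1.3).** For Part I: "Dose levels which are higher than the recommended dose in trial 1336-0001 (720 mg) will not be investigated". Below that ceiling there is room: "Intermediate or lower dose levels may be investigated if agreed in the SMC", and for Part II "The dose of BI 754091 may also be titrated based on DLTs and the overall safety profile of the combination". On the top Part II level: "For dose level 2, level 2-a or 2-b will be investigated based on the information from trial 1336-0011".

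**Conclusions drawn.** Sections 10.5.1 and 10.5.2 say the simulated mean sizes support planned maxima of 9 and 12 patients, and both claim good precision in finding the MTD. Section 7.6 expects about 9 and about 15 patients, with more possible.

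**The concern.** An MTD can only be declared at a dose in the simulated set. A non-zero percentage in a category that no listed dose belongs to shows that the results come from a different set. For Part I the footnote says which one; for Part II nothing in the current text does.

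The appendix offers these tables, with the data scenarios, as its evidence on accuracy, stopping and size. A reader will take 42% and 49% as the chance of ending with no tolerable dose when every listed dose is too toxic. The text on Part I scenario 6 does not mention that 120 mg was available to the model. The size sentences are a separate difficulty: a mean above the stated maximum cannot show that the maximum is reasonable.

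**Working it through.** **1. Classify the listed rates.** Sections 7.1.1 and 7.1.2 define under [0, 0.16), target [0.16, 0.33), over [0.33, 1].

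| Printed cell | Listed true rates | Categories possible |
|---|---|---|
| Part I scenario 1, overdose 25.7% | 0.069, 0.154 | under |
| Part I scenario 5, overdose 5.3% | 0.180, 0.317 | target |
| Part I scenario 6, target 46.4% | 0.580, 0.769 | over |
| Part II scenario 1, underdose 5.9% | 0.209, 0.318, 0.680 | target, over |
| Part II scenario 6, target 24.4% | 0.489, 0.580, 0.769 | over |

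The 500/240 level, absent from Table 10.5.2: 2, cannot explain the Part II cells: its rate lies between those of 360/240 and 720/240.

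**2. Cross-check on printed DLT counts.** Mean DLTs must lie between (lowest rate × mean N) and (highest rate × mean N).
- Part I scenario 1: at most 0.154 × 11.4 = 1.8; printed 2.3.
- Part I scenario 6: at least 0.580 × 8.7 = 5.0; printed 4.1.
- Part II scenario 6: at least 0.489 × 11.0 = 5.4; printed 4.3.

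**3. Part I rerun.** The decision tree was enumerated with the Table 7.1.1: 2 prior. Assumptions: cohorts of 3; EWOC limit 0.25; next dose is the one with the highest target probability among those passing EWOC; no skipping of untested levels; MTD declared on either Section 7.1.1 criterion; trial stopped if no dose passes. Entries are under/target/over/stopped, %.

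| Scenario | Printed | Rerun, added level in | Rerun, 360/720 mg only |
|---|---|---|---|
| 1 | 72.6/0/25.7/1.7 | 70.9/0/27.6/1.5 | 98.5/0/0/1.5 |
| 5 | 0/83.3/5.3/11.4 | 0/80.2/8.3/11.5 | 0/88.5/0/11.5 |
| 6 | 0/46.4/11.6/42.0 | 0/46.8/10.9/42.3 | 0/0/10.6/89.4 |

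With the added levels these rows come back within 3 points; a repeat of scenario 6 with 120 mg gave about 39% stopped. On 360/720 mg, scenarios 2 to 4 barely move: 0/38.0/22.5/39.5, 11.8/87.6/0/0.5 and 0/28.6/45.4/25.9. In scenario 3 with 1250 mg included, however, 44.5 of the 87.9 target points are at 1250 mg.

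*Sensitivity.* The printed prior does not return rows 1 to 5 of Table 10.5.1: 1 (row 2: 0.575/0.294/0.131 against 0.406/0.416/0.179; row 3 overdose probability: 0.388 against 0.241). A second prior was therefore fitted that returns all six rows within 0.02. Scenario 6 stopping on 360/720 mg is then:
- printed prior: 89.4%; 87.9% if the trial must stay at 360 mg after 2 DLTs in 3; 98.2% if both MTD criteria are required;
- fitted prior: 88.4% (either criterion); 91.0% (both).

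**4. Part II scenario 6, lower bound on stopping.** After 2 DLTs in 3 at 120/240, Section 10.5.2 says "the model recommends stopping the trial because of high overdose probabilities". After 1 in 3, Table 10.5.2: 1 repeats 120/240. At a rate of 0.489:
- P(at least 2 of 3) = 3 × 0.489² × 0.511 + 0.489³ = 0.4835
- P(1 of 3) = 3 × 0.489 × 0.511² = 0.3831
- P(1 of 3, then at least 2 of 3) = 0.3831 × 0.4835 = 0.1852
- Sum = 0.669

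The second path needs 120/240 to fail EWOC after 3 DLTs in 6. The posterior overdose probability there is 0.69 with Table 7.1.2: 5 as labelled, and 0.52 with its two compounds' rows exchanged. If 1000 trials were run, as in Part I, the standard error of 49.1% is √(0.491 × 0.509/1000) = 0.0158, so the gap is (0.669 − 0.491)/0.0158, about 11 standard errors.

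**5. Part II full rerun.** Exchanging the compound rows of Table 7.1.2: 5 returns the means in Table 7.1.2: 6 and all six rows of Table 10.5.2: 1 within 0.01, so that version was used, with the printed escalation after 0 in 3 imposed. Scenario 6 stopping is 90.0% (either criterion) or 90.6% (both). The result is the same on 120/360/500 and 120/360/720, for any 500/240 rate between 0.580 and 0.769. Without imposing that escalation it is 93.0%; with the rows as labelled, 93.5% and 96.1%.

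In scenarios 4 and 5 only 720/240 (rates 0.505 and 0.550) can produce the printed overdose percentages, 20.8% and 23.4%. In the reruns it is declared MTD in at most 0.3% and 1.3% of trials.

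**6. Size and precision.**
- Part I printed means exceed 9 in four of six scenarios (11.4, 11.7, 9.3, 10.3), with a range to 33.
- Part II's largest mean is 14.6, with a range to 42.
- Part II scenarios 3 to 5 each contain a combination in the target interval (rates 0.190, 0.290, 0.169), yet the printed target percentages are 29.2%, 7.5% and 10.6%.

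**The case against.** The three Part I cells come from levels the footnote discloses with every assumed rate, so they are correct results for that dose set. This stands: the fault is pooling and presentation, not miscalculation. The 120 mg level also differs from 1250 mg, since Section 4.1.3 allows lower levels if the SMC agrees, so 42.0% describes a possible path. The roughly 90% figure applies only to the listed levels.

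For Part II, the Amendment 2 log records that tables for BI 754091 80 and 400 mg were removed from Table 10.5.2: 2. Table 10.5.2: 3 may still reflect the larger set. This is plausible but cannot be tested, because those rates are not given. It would explain the mismatch without making the current tables agree.

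The rerun percentages depend on assumptions. The sponsor's stopping code is unknown: the printed range to 33 is not reproduced when either criterion suffices, and the Part II rerun needs exchanged prior rows. That is fair, and only the five cells and the DLT-count check need no modelling.

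More stopping in scenario 6 is also the right outcome, since every listed dose is too toxic, so the printed rows do not flatter the design. On 360/720 mg the rerun mean size is 4.9 to 9.5 when either criterion suffices, which is compatible with about 9; if both are required it reaches about 29. Finally, Part II uses dummy data to be replaced, and no dosing decision rests on these tables.

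**Conclusion.** The concern holds. Five printed cells are impossible for the listed levels; this is exact and follows from the printed rates and intervals. Stopping in scenario 6 is understated for those levels. In Part I it is 88% to 98% over two priors and two MTD stopping rules, against 42.0% printed. In Part II it is at least 66.9%, and 90% to 96% on full reruns, against 49.1%. These figures assume cohorts of 3 and no use of lower levels or BI 754091 titration.

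The Part I maximum of 9 does not follow from the printed means. The Part II maximum of 12 fails on the same ground and conflicts with Section 7.6. The precision statement is not supported by Part II scenarios 3 to 5. EWOC, the dose ceiling and SMC review are unaffected: this is a moderate reporting error that should be fixed, not a risk to conduct.

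**What to change.** - Rerun Part I on 360/720 mg.
- Rerun Part II as two three-level sets, 120/360/500 and 120/360/720 with BI 754091 at 240 mg, because Section 4.1.3 makes levels 2-a and 2-b alternatives. State the rate assumed for 500/240.
- State the prior, cohort size and stopping rule simulated, and report selection by dose level.
- Show any level outside Tables 4.1.3: 1 and 4.1.3: 2, including lower BI 836880 levels or a titrated BI 754091 dose, only as a separate labelled run.
- Restate or delete the two precision statements.
- Replace the maxima of 9 and 12 with expected sizes reconciled with Section 7.6.

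Cost: a few hours of simulation and appendix text, with no extra patients and no change to trial conduct. The overdose percentages in Part I scenarios 1 and 5 would fall to zero, and scenario 6 would show more stopping, which is the desirable result there.
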